2.2.5.2 Good Laboratory Practice 1-Month Toxicology Studies (Rat and Monkey)

The toxicology of AZD4573 has been evaluated in repeat dose cycle IV infusion studies of up to 1-month duration in rats and cynomolgus monkeys. A non-Good Laboratory Practice (GLP) in vitro genotoxicity study was also conducted.

Key findings from these studies are summarised below:

- Dose-related decreases in peripheral white blood cell parameters, particularly neutrophils or lymphocytes, were noted in the rat and cynomolgus monkey following repeated dose cycle administration of AZD4573. The DLT in the rat was severe neutropenia with resulting disseminated bacterial colonies in several tissues. These white blood cell decreases were related to the primary pharmacological action of AZD4573 and showed evidence of partial recovery between dose cycles and at the end of the 16-day recovery period.
- The principal histopathological finding in the 1-month repeat dose cycle toxicology studies was dose-dependent decreased cellularity of lymphoid tissues and bone marrow, which are consistent with the primary pharmacological action of AZD4573. Decreased cellularity was seen in the thymus, spleen, and lymph nodes of rats and cynomolgus monkeys, and in the bone marrow and Peyer's patch of rats only. Reversibility of the bone marrow findings was seen at the end of the 16-day recovery period, but mild decreases in lymphoid tissue cellularity were still present in both species at the end of the recovery period.
- Repeated dosing of AZD4573 to the cynomolgus monkey was associated with dose-limiting emesis and diarrhoea at 1.0 mg/kg and above. No test article-related histopathological changes were seen in the gastrointestinal tract in the monkey dose range finding and 1-month studies.
- Exocrine pancreatic acinar cell atrophy and/or vacuolation were seen at ≥ 0.5 mg/kg in the cynomolgus monkey 1-month toxicology study. In the rat, repeat dosing of AZD4573 showed vascular fibrinoid necrosis, interstitial oedema, fibrino-haemorrhagic inflammation or acinar cell apoptosis in the pancreas at ≥ 8.0 mg/kg. Transient increases in amylase and lipase correlated with the observed histopathological changes. Reversibility was noted at the end of the 16-day recovery period in the rat, but mild acinar cell atrophy was still present in the monkey.

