	Alanine transaminase and aspartate transaminase	$< 3.0 \times \text{ULN}$
Renal	Calculated creatinine clearance by Cockcroft Gault equation $[(140-\text{Age}) \cdot \text{Mass (kg)} / (72 \cdot \text{creatinine mg/dL}) \cdot \text{multiply by 0.85 if female}]$	$\geq 60 \text{ mL/minute}$
Coagulation	INR	$< 1.5 \times \text{ULN}$
Pancreatic	Lipase	$\leq 3.0 \times \text{ULN}$ and no ongoing pancreatitis
	Amylase	$\leq 3.0 \times \text{ULN}$ and no ongoing pancreatitis
Cardiac	LVEF as assessed by echocardiography MUGA ^b	$\geq 40.0\%$

^a Gilbert's syndrome = ratio between total and direct bilirubin > 5 .

^b Appropriate correction to be used, if a MUGA is performed.

Abbreviations: INR = International Normalised Ratio; LVEF = left ventricular ejection fraction; MUGA = multigated acquisition scan; ULN = upper limit of normal.

- 7 Uric acid level $<$ upper limit of normal (ULN). If hyperuricaemia is present at Screening, SoC therapy for hyperuricaemia should be administered (including IV fluid and rasburicase or allopurinol) to reduce the uric acid levels to $<$ ULN before the start of study intervention.
- 8 Willing and able to participate in all required evaluations and procedures in this study protocol including swallowing capsules intact without difficulty, receiving IV administration of study drug and being admitted, when required, for up to 24 hours during study drug administration.

Sex

- 9 Male or female.

Reproduction

Contraceptive use by men or women should be consistent with local regulations regarding the methods of contraception for those participating in clinical studies. Male participants must be willing to use barrier contraception (ie, condoms) and female partners should use highly-effective methods of contraception for the duration of the study and for a washout period of 4 months for men and 7 months for women after discontinuing AZD4573.

A more detailed description of the required lifestyle restrictions relating to reproduction is provided in Section [5.3.1](#).

- 10 Negative pregnancy test (serum) at Screening for female participants of childbearing potential.
- 11 Female participants should not be breastfeeding.
- 12 Female participants must be one year post-menopausal, surgically sterile, or using one highly-effective form of birth control (the participant should have been stable on their chosen method of birth control for a minimum of 3 months before entering the study and continue to 7 months after the last dose).

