- ^o All participants will receive TLS prophylaxis during the intra-patient ramp up and be monitored for TLS during the first 24 hours post start of dose; this requirement will continue until they have received at least one AZD4573 dose at the target dose level (i.e., for at least the first 3 AZD4573 once-weekly doses). TLS monitoring will be performed at the following timepoints: predose AZD4573, 6 h after the start of the infusion, and 24 h (\pm 1 h) after the start of the infusion. Participants showing signs of clinical or laboratory TLS at 6 h after start of infusion must be admitted for in-patient TLS monitoring for a minimum of 24 h after the start of the infusion and monitored every 4 to 6 h during this time (or more frequently if clinically indicated). For each TLS monitoring timepoint, a TLS Monitoring page in the eCRF is to be filled out. Fluid balance must be monitored according to local institutional standards.
- ^p Urine samples will be collected at the following timepoints: Screening, Cycles 1-8, predose AZD4573 (within 72 hours prior to infusion) and within approximately 2 hours after the end of infusion, Cycles 9+ on Day 1 of each cycle, predose AZD4573 and within approximately 2 hours after the end of infusion, and at the 30-day SFU.
- ^q Pregnancy test to be performed at Screening (serum) and predose (serum or urine) on Cycle 1, Week 1, then once every 21 days (\pm 7 days) prior to initiating a new cycle and at the 30-day SFU visit. Additional testing may be performed at Investigator discretion (eg, in the event of suspected contraception failure).
- ^r Lipase and amylase should be evaluated at Screening, Cycles 1-8 predose AZD4573 (within 72 hours prior to infusion), Cycles 9+, predose AZD4573 (within 72 hours prior to infusion) on Day 1 of each cycle, and at the 30-day SFU visit.
- ^s In addition to hepatitis serology as specified, participants who are anti-HBc positive, or have a known history of HBV infection, should be monitored every 3 months with a quantitative PCR test for HBV DNA. In addition, any participants testing positive for any hepatitis serology must have PCR testing for verification purposes.
- ^t CD4, CD8, CD19, CD16/NK and serum immunoglobulins (IgA, IgM, IgG) will be drawn at Screening, Day 1 (predose) of Cycles 2, 4, 7, 9, 13, 16, 19 and every 6 months thereafter (predose), and at the 30-day SFU.

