ff A biopsy will be taken at disease progression for participants who consent. The disease progression sample may be taken at the SFU visit if not collected previously.

gg Bone marrow biopsy and aspirate: **CCI**

hh See [Table 19](#) for schedule of disease assessments, including mandatory PET assessments. Disease assessments will be done by the Investigator using the Lugano Response Criteria for Non-Hodgkin's Lymphoma ([Cheson et al 2014](#)). Additional disease assessments may be performed as clinically indicated.

ii Acalabrutinib 100 mg oral capsule to be given twice per day.

jj AZD4573 is to be administered as an absolute (flat) dose, 2-h (\pm 15 mins) IV infusion on a once-weekly schedule.

kk Participant-reported drug administration for acalabrutinib needs to be done on every AZD4573 dosing day, ideally prior to dosing (\pm 24 h) and is also to be done after the last acalabrutinib capsule is taken and the leftover capsules returned to site. Drug accountability for acalabrutinib will occur every 2 weeks, (on an AZD4573 dosing day, ideally prior to dosing [\pm 24 h]).

ll If a participant is attending Cycle 9+ visits according to a modified schedule, in which AZD4573 is not infused and assessments are not performed every week, the Day 1 assessments should be performed at least once per cycle.

mm The End of Treatment visit is the last visit attended by the participant prior to the 30-Day SFU on the study. At this visit, the participant does not receive IMP and should undergo the applicable assessments associated with the Cycle and visit they have reached, plus those shown in the "Disease Assessment/End of Treatment" column of the SoA.

nn AZD4573 should be administered at least 5 days apart.

Abbreviations: ACTH = adrenocorticotropic hormone; BID = twice daily; CMV = cytomegalovirus; CPK = cyclin-dependent kinase; CSP = clinical study protocol; ECG = electrocardiogram; eCRF = electronic case report form; ECHO = echocardiogram; ECOG = Eastern Cooperative Oncology Group; GLDH = glutamic dehydrogenase; Ig = immunoglobulin; **CCI** [REDACTED] LDH = lactate dehydrogenase; LTFU = long-term follow-up; **CCI** [REDACTED]; MUGA = multigated acquisition; **CCI** [REDACTED]; PCR = polymerase chain reaction; PK = pharmacokinetics; SFU = safety follow-up; SoC = standard of care; T4 = thyroxine; TLS = tumour lysis syndrome; TSH = thyroid-stimulating hormone.

Table 5 Schedule of Activities: Module 1 (AZD4573 with Acalabrutinib) Part B – Expansion

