15.3 Definition of Dose-limiting Toxicity (DLT)

A Dose Limiting Toxicity is defined as any event that meets the DLT criteria listed in this section, unless unequivocally due to underlying malignancy or an extraneous cause.

Any participants receiving AZD4573 beyond the dose escalation/DLT-assessment period will be monitored for safety using the same DLT criteria used during the DLT-assessment period.

The SRC will make a recommendation to stop or continue recruitment after review of the data from each cohort (see Section [18.6](#)).

The DLT-assessment period applicable in Part A of this module is normally 5 weeks (DLT observation will continue throughout the study for Part A and Part B). Any participant who does not complete the DLT-assessment period in Part A may be replaced, with the exception of a participant who experiences a DLT; these participants will not be replaced.

Additional participants enrolled at a previously-cleared dose level to provide supplemental safety, efficacy, PK, and pharmacodynamics data will not be replaced or evaluated for DLT in support of dose-escalation decisions. However, these additional participants will be included in the determination of MTD/RP2D at the end of the dose-escalation process.

Any AE that meets the DLT criteria in the opinion of the principal Investigator should be reported to the Medical Monitor within 24 hours of knowledge of the event.

A DLT will be defined as the occurrence of any of the following, unless unequivocally due to underlying malignancy or an extraneous cause:

DLT criteria (CTCAE version 5.0):

- Any Grade ≥ 3 non-haematological toxicity except:
 - Grade 3 nausea, vomiting, or diarrhoea despite premedication that respond to medical management (eg, improve by 1 or more severity grade within 72 hours of onset of toxicity, or 96 hours [-2/+12 hours] from the start of dose, whichever is the sooner).
 - Grade ≥ 3 serum lipase and/or amylase that return to initial eligibility criteria within 72 hours of onset of toxicity or 96 hours (-2/+12 hours) post start of dose, whichever is the sooner. Grade ≥ 3 serum lipase and/or amylase that do not return to meet initial eligibility criteria within 72 hours of onset of toxicity or 96 hours (-2/+12 hours) post start of dose, whichever is the sooner, will be considered a DLT.

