17.1.6 Clinical Safety Laboratory Assessments

For all participants, results of safety laboratory testing (haematology and clinical chemistry at a minimum) must be available within 72 hours prior to dosing and must be reviewed by the Investigator prior to administration of AZD4573 (all cohorts). If clinically indicated, additional clinical laboratory tests and evaluations may be performed by the Investigator (eg, additional haematology/clinical chemistry panels, TLS parameters, liver enzyme tests); these need to be entered into the eCRF.

This study will use local laboratories.

The following laboratory variables will be measured:

Haematology: complete blood count (CBC) with automated and/or manual differential including, but not limited to, white blood cell count, haemoglobin, haematocrit, platelet count, ANC, and absolute lymphocyte count (ALC), and blast cells. Haematology should be evaluated before dosing while participants are receiving treatment.

Haematology samples will be collected at the following timepoints:

- Screening
- Cycles 1, 2, and 3
 - Predose AZD4573 (within 72h prior to infusion)
 - 24 hours after the start of the infusion
- Cycles 4+
 - Predose AZD4573 (within 72 hours prior to infusion)
 - If clinically indicated, 24 hours after the start of the infusion
- 30-Day SFU

The Investigator may take additional, unscheduled samples throughout the study if deemed clinically warranted and these need to be entered into the eCRF.

Haematology tests do not need to be repeated before first dose if the first-dose visit is within 3 days of the Screening sample.

Clinical Chemistry: albumin, chloride, bicarbonate, calcium total, magnesium, phosphorous, glucose (fasting preferred), CK, ALP, ALT, ammonia (where available at local institution; to be tested every 2 weeks), AST, urea, , cholesterol, C-reactive protein, creatinine, Factor V (where available at local institution), GGT, lactate dehydrogenase (LDH), phosphate, potassium, sodium, triglycerides, total bilirubin, direct and indirect bilirubin, total protein, uric acid.

Clinical chemistry samples will be collected at the following timepoints:

- Screening
- Cycles 1, 2, and 3
 - Predose AZD4573 (within 72 hours prior to infusion)
 - 24 hours after the start of the infusion
- Cycles 4+

- Predose AZD4573 (within 72 hours prior to infusion)
- If clinically indicated, 24-hour after the start of the infusion
- 30-Day SFU

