If an unscheduled ECG is done at any time, then an electrolyte panel (ie, calcium, magnesium, potassium), and troponin must be done to coincide with the ECG testing.

Supra-renal glands: T4, cortisol, adrenocorticotropic hormone (ACTH) and thyroid-stimulating hormone (TSH) should be measured at the following timepoints:

- Screening
- Cycle 2 Day 1
 - Predose AZD4573 (within 72 hours prior to infusion)
- 30-Day SFU

Pancreas: Lipase and amylase measurements are required at the following timepoints:

- Screening
- Cycles 1 through Cycle 8
 - Predose AZD4573 (within 72 hours prior to infusion)
- Cycles 9+ on Day 1 of each Cycle
 - Predose AZD4573 (within 72 hours prior to infusion)
- 30-Day SFU

Lipase/amylase tests do not need to be repeated before first dose if the first-dose visit is within 3 days of the Screening sample.

TLS monitoring will include: potassium, calcium, phosphate, uric acid, and creatinine.

TLS monitoring will be performed at the following timepoints:

- Cycle 1, Weeks 1 through 3
 - Predose AZD4573
 - 6 hours (\pm 30 minutes) after the start of the infusion
 - 24 hours (\pm 1 hour) after the start of the infusion (and prior to acalabrutinib dosing)

Participants showing signs of clinical or laboratory TLS at 6 hours after the start of the infusion must be admitted for in-patient TLS monitoring for a minimum of 24 hours after the start of the infusion and monitored every 4 to 6 hours during this time (or more frequently if clinically indicated).

For each TLS monitoring timepoint, a TLS Monitoring page in the eCRF is to be filled out.

Hepatitis serology will be conducted at Screening. Hepatitis serology must include hepatitis B surface antigen (HbsAg), hepatitis B surface antibody (anti-HBs), anti-HBc, and hepatitis C (HCV) antibody. Participants who are anti-HBc positive, or have a known history of hepatitis B virus (HBV) infection, should be monitored every 3 months with a quantitative PCR test for HBV DNA (Section 17.1.10.4). In addition, any participants testing positive for any hepatitis serology must have PCR testing for verification purposes.

Pregnancy: a sample for a pregnancy test will be collected from all female participants of childbearing potential at:

- Screening (serum)
- Cycle 1, Week 1

- Predose
- Cycles 2+ once every 21 days (\pm 7 days) prior to initiating a new cycle
- 30-day SFU visit

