Pregnancy tests after Screening may be serum or urine. Urine β -hCG and quantitative serum β -hCG tests are permitted. If a urine β -hCG test is positive or indeterminate, quantitative serum β -hCG will be performed for confirmation. Additional testing may be performed at Investigator discretion, for example in the event of suspected contraception failure.

Liver chemistry tests: For any participant on study who experiences elevated ALT /AST $\geq 3 \times$ ULN and/or elevated total bilirubin $\geq 2 \times$ ULN: repeated liver chemistry tests (INR, fibrinogen, D-dimer [where available at institution], ALP, ALT, AST, GLDH, CPK, total bilirubin, direct bilirubin, indirect bilirubin) are required at 48 hours (-2/+12 hours) and 96 hours (-2/+12 hours) after the start of the infusion and every 48 hours (-2/+12 hours) thereafter until resolution of the event. If an event is not resolved within 96 hours the medical monitor shall be contacted. If GLDH cannot be performed locally, LDH will be analysed locally and a serum sample must be collected for central retrospective GLDH analysis. Refer to the Laboratory Manual for details.

During the course of the study the Investigator will remain vigilant for increases in liver biochemistry. The Investigator is responsible for determining whether a participant meets PHL criteria at any point during the study. The Investigator participates, together with the Sponsor, in review and assessment of these cases. Hy's Law (HL) criteria are met if there is no alternative explanation for the elevations in transaminases and total bilirubin levels.

If an unscheduled ECG is done at any time: troponin and an electrolyte panel* must be done to coincide with the ECG testing.

* can include: sodium, calcium, potassium, chloride, phosphate, magnesium.

If a participant is assessed as meeting PHL criteria, please refer to [Appendix E](#).

CMV: All subjects will have CMV testing at Screening including serology testing for CMV immunoglobulin (Ig)G and CMV IgM and CMV DNA PCR testing. Subjects must have a negative result for CMV DNA PCR such that CMV DNA is not detected by PCR at Screening, to be eligible for the study. The Screening CMV serologies will be advisory only, to guide investigators in assessing the risk of new infection or reactivation of CMV while on study.

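### The lipase/amylase DLT rule uses a 72 h/96 h recovery deadline, but the enzymes are scheduled only pre-dose, so a Grade 3 or higher rise that outlasts the deadline and settles before the next draw is counted as no DLT

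*Protocol*

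**What the plan says.** Section 15.3 lists Grade 3 or higher lipase or amylase among the exceptions to the non-haematological DLT rule when the values recover in time. They become a DLT when they "do not return to meet initial eligibility criteria within 72 hours of onset of toxicity or 96 hours" (-2/+12 h) after the start of dose, whichever is sooner. The recovery level comes from Table 2 in Section 5.1: each enzyme at or below 3.0 x ULN "and no ongoing pancreatitis".

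The sampling plan is in two places. Table 4 (Section 10.2, footnote r) says "Lipase and amylase should be evaluated at Screening, Cycles 1-8 predose AZD4573 (within 72 hours prior to infusion"), and Table 5 repeats this for Part B. Section 17.1.6, under Pancreas, says "Lipase and amylase measurements are required at the following timepoints" and then lists Screening, pre-dose and the 30-day safety follow-up, with no post-dose time.

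Two other panels in Section 17.1.6 could have filled the gap. Clinical chemistry is drawn 24 h after the start of infusion in Cycles 1 to 3, but its analyte list has neither enzyme. Repeat tests triggered by raised ALT, AST or bilirubin are taken at 48 h and 96 h "after the start of the infusion and every 48 hours (-2/+12 hours) thereafter until resolution of the event", and that panel omits both enzymes too.

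At the end of Section 15.3, the second item under what the DLT definition excludes removes isolated laboratory changes of any grade that have no clinical consequence or significance. It exempts only the transaminase and bilirubin abnormalities.

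**The concern.** The criterion asks two things of the data: when the rise began, and whether it had settled by a stated hour. A pre-dose sample up to a week after the last infusion generally answers neither. The liver criteria in the same section also use hour-based limits, but the protocol supports those with samples at 24 h, 48 h and 96 h. The pancreatic criterion has no such support.

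DLTs are a Part A primary endpoint (Table 7) and the input to every Table 11 action. The same criteria feed the rule in Section 15.2 that may pause expansion enrolment when more than 30% of participants have a qualifying event. Pancreatic injury is a listed potential risk (Section 2.3.1). In the animal studies, Section 2.2.5.2 reports "Transient increases in amylase and lipase correlated with the observed histopathological changes", a time course that pre-dose sampling is poorly placed to catch.

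**Working it through.** **Inputs.** Deadline: 72 h from onset or 96 h (-2/+12 h) from dose start, whichever is sooner (15.3). Pre-dose window: up to 72 h before infusion (Table 4; 17.1.6). Dosing: weekly, 168 h nominal, and "AZD4573 should be administered at least 5 days apart", so at least 120 h. Escalation rule: mTPI-2, target 30% ± 5%, unsafe cut-off 95% (13.1, 15.2).

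**Step 1: reproduce Table 11.** A Beta(1,1) prior is assumed, giving a posterior Beta(1+x, 1+n−x) for x DLTs in n. A dose is unsafe if P(p > 0.30) > 0.95. Otherwise the action is that of the sub-interval, in steps of 0.10 around 0.25–0.35, with the largest unit probability mass. All 43 cells for n = 3 to 9 and 0 to 6 DLTs match. At n = 1 and 2 the only differences are those that the table's footnotes a and b declare. As an example, 3/3 gives 1 − 0.30⁴ = 0.9919, hence DU. For 2/3, 1 − (4×0.30³ − 3×0.30⁴) = 0.9163, which is not DU; the table shows D.

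**Step 2: when the sample falls.** Time after the previous dose = (interval − 72 h) to interval.

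- Weekly: 168 − 72 = 96 h, to 168 h.
- Five-day minimum: 120 − 72 = 48 h, to 120 h.
- Nine-day gap (an assumed late visit): 216 − 72 = 144 h, to 216 h.

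**Step 3: blind interval.** Deadline = min(onset + 72, 96) h. A qualifying rise is missed only if it falls below Grade 3 or recovers after the deadline and before the sample. The length of that interval is sample time − deadline:

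| Onset after dose | Deadline | Sample at 96 h | Sample at 120 h | Sample at 144 h | Sample at 168 h |
|---|---|---|---|---|---|
| 0 h | 72 h | 24 h | 48 h | 72 h | 96 h |
| 6 h | 78 h | 18 h | 42 h | 66 h | 90 h |
| 24 h or later | 96 h | 0 h | 24 h | 48 h | 72 h |

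Where the 96 h limit binds and the full +12 h tolerance is used, the last entry becomes 168 − 108 = 60 h.

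**Step 4: what one missed DLT does in Table 11.**

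- n = 3: 1 read as 0, Stay becomes Escalate.
- n = 5: 2 read as 1, De-escalate becomes Escalate.
- n = 6: 2 read as 1, Stay becomes Escalate; 3 read as 2, De-escalate becomes Stay.

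**Step 5: illustration only.** Let m be the share of all DLTs that is missed. The protocol gives no basis for m, so the values below are assumptions. With a true DLT rate of 40%, the observed rate is 0.40(1 − m). For a single look, P(Escalate) is P(0 DLTs) at n = 3 and P(0 or 1 DLT) at n = 6:

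| m | n = 3 | n = 6 |
|---|---|---|
| 0% | 21.6% | 23.3% |
| 5% | 23.8% | 26.6% |
| 10% | 26.2% | 30.1% |
| 25% | 34.3% | 42.0% |

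**Step 6: the two parts of Section 15.3 side by side.** The criterion says that an enzyme rise not settled in time will count as a DLT. The second exclusion, read literally, removes the same rise if it is isolated and clinically silent, because lipase and amylase are not among its exemptions. Both cannot apply to the same participant.

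**The case against.** A reader might infer that every qualifying lipase or amylase event goes unseen. The documents do not support that. Qualifying events are by definition the persistent ones. One still at Grade 3 or higher at a pre-dose draw at or after 96 h is measured, and its timing shows that the deadline has passed. A rise that recovers in time is not a DLT, so missing it costs nothing. Nor is it right that no scheduled sample can ever bear on the deadline: draws at 96 to 108 h lie inside the stated tolerance, and five-day spacing allows a draw at 48 h.

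There are also safeguards. Section 17.1.6 says "If clinically indicated, additional clinical laboratory tests and evaluations may be performed by the Investigator", and Section 4.1 has a similar provision. The Safety Review Committee judges whether safety assessments were sufficient (Section 15.6) and is guided by mTPI-2 rather than bound to it (Section 15.2). These help, but none requires a test in a participant without symptoms.

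The clinical evidence is reassuring as far as it goes. Section 17.1.10.14 reports no clinical data suggesting pancreatic injury so far, and the first-in-human DLTs listed in Section 2.2.6 include no pancreatic event. The transient rises are animal findings. Finally, Section 4.1 says that recruitment has stopped, so new Cycle 1 samples would reach no new participant. Both points stand. They limit the likely effect and move the remedy towards reporting, but they do not make the criterion workable as written.

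**Conclusion.** The point holds in a limited form. The lipase/amylase criterion cannot be applied in full from scheduled samples. Onset cannot be dated, and a Grade 3 or higher rise that passes the deadline but falls below Grade 3 or recovers before the next pre-dose draw is not observed and enters the count as no DLT. At weekly dosing the blind interval runs from 0–24 h (draw at 96 h) to 72–96 h (draw at 168 h), before the +12 h tolerance.

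The direction is downward. The size cannot be calculated, because the protocol gives neither an event rate nor a human time course for these enzymes. The Table 11 changes show sensitivity to one missed event, not evidence that one was missed. The conclusion also depends on how the conflict within Section 15.3 is settled: if the second exclusion governs, the clinically silent rises are not DLTs however they are sampled. No sample-size or power figure is affected.

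**What to change.** 1. Reconcile the lipase/amylase criterion in Section 15.3 with the second exclusion in the same section, and align both with the schedules in Tables 4 and 5 and Section 17.1.6. This is a text change. Which reading applies is for the sponsor and the Safety Review Committee.

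2. For any further dosing under these DLT criteria, add lipase and amylase to the 24 h chemistry draw already made in Cycles 1 to 3. If the value is Grade 3 or higher, repeat at the 48 h and 96 h (-2/+12 h) times already used for liver chemistry. The cost is two analytes at an existing draw, a few triggered samples and one line in each schedule. It is not a complete cure: a rise starting after 24 h triggers no repeat, and a deadline between the two repeats (78 h for onset at 6 h) is still not resolved exactly.

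3. Because recruitment has stopped, the step with most effect now is in the report. State that lipase/amylase DLTs resolving between the deadline and the next pre-dose sample could not be observed, and do not present their absence as no DLT without that qualification. Rises still present at the pre-dose draw remain assessable and should be reported as such. This costs a sentence.
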